5.5.3 Handling of study treatment

5.5.3.1 Handling of investigational treatment

Investigational treatment must be received at the study site by a designated person, handled and stored safely and properly, and kept in a secured location to which only the Investigator and designated staff have access. Upon receipt, the study drugs should be stored according to the instructions specified on the labels.

Storage conditions must be adequately monitored and appropriate temperature logs maintained as Source data.

The Investigator must maintain an accurate record of the shipment and dispensing of study

drug in a drug accountability ledger. Drug accountability will be noted by the Monitor during site visits and/or at the completion of the trial.

All drug supplies are to be used only for this protocol and not for any other purpose. Unless specifically instructed by Novartis, the Investigator must not destroy any drug labels, or any partly used or unused drug supply.

At the conclusion of the study, and, if allowed during the course of the study (e.g., an open-label study or an unblinded monitor), the Investigator will provide a copy of the drug accountability ledger to the monitor.

Only after receiving a written authorization by Novartis, the Investigator/designee will send all the unused and partly used drug supplies as well as the empty containers to the address provided at the time of authorization for destruction, or have the unused and partly used drug supplies as well as the empty containers destroyed by the site's pharmacist, providing a drug destruction certificate.

5.5.4 Instructions for prescribing and taking study treatment

The Investigator will dispense the appropriate amount of study drugs to cover each visit and additional drug in case of loss, breakage, or scheduling problems. Drug accountability will be performed to assess compliance. The Investigator should promote compliance by instructing the patient to take the study drug exactly as prescribed and by stating that compliance is necessary for the patient's safety and the validity of the study. The patient should be instructed to contact the Investigator if he/she is unable for any reason to take the study drugs as prescribed.

If MMF, Tac and/or CS are part of the assigned regimen, they will be taken concomitantly as per standard of local practice. The study drugs may be taken with or without food, but in a consistent fashion. Special attention must be taken to avoid concomitant administration of drugs, food or beverages which are known to be a strong inducer or inhibitor of CYP3A4 (see [Appendix 5](#)).

All drug trough levels assessed in this study (CFZ533, Tac, MPA) will be measured per the [Assessment schedule](#) or as per local practice (Tac/ MPA). For all samples sent for central analysis, the exact time and the date of sampling, together with the exact time and date of the last study medication dose prior to the sampling must be recorded on the central laboratory request form (refer to the separate Laboratory Manual). CFZ533 and MPA will be measured in plasma and Tac will be measured in whole blood samples. The patient will be instructed not to take his/her morning dose of immunosuppressant medications the day of a scheduled sampling, to record the medication dosage and time of last dose on the day prior to the blood sampling, and to bring all study drugs to the visit so that a dose may be administered upon completion of blood sampling.

All dosages of CFZ533 (all parts), MMF and Tac and all dose changes during the study must be recorded, with reason for administration, on the corresponding Dosage Administration Record eCRF.

All immunosuppressive drugs used and dosages administered must be recorded during the study. All changes to the immunosuppressive medication dosing regimen should be recorded

in the appropriate eCRF, along with the reason for change and dates.

Induction therapy, pre and post-transplant immunosuppression

For patients randomized to the control arm or where Tac, MMF and/or steroids are to be administered per protocol, they may be administered prior to transplant according to center practice but such practice must be applied consistently to all subjects at a given center. At randomization/enrollment, all subjects must follow the assigned regimen. Pre-transplant immunosuppression, including induction therapy and any Tac or MMF should be recorded on the Concomitant medication eCRF under the Immunosuppressive category.

Basiliximab induction therapy

Subjects randomized to receive induction therapy will receive 2 x 20 mg doses of basiliximab administered IV. The first dose should be given within 2 hours prior to transplant surgery, and the second dose should be administered on Day 4 post-transplant, or according to local practice.

The 20 mg vial should be reconstituted with 5 mL sterile water. The resultant solution is isotonic and may be injected as an IV bolus. Alternatively, the solution may be diluted to a volume of 50 mL with sterile saline and 5% dextrose and administered as an infusion over 30 minutes. If venous irritation occurs following bolus administration, the next dose (if appropriate) should be administered as a 30 minute infusion. There is no maintenance dose, and no other antibodies are permitted for induction therapy. All basiliximab doses and changes must be recorded in the Concomitant Medications eCRF under the Immunosuppressive category.

CFZ533 therapy

CFZ533 will be administered by IV infusion or SC injection to the patient by authorized Investigator staff at each visit specified in the [Assessment schedule](#).

The first dose of CFZ533 will be administered IV pre-transplant or intra-operatively. Drug administration will begin after randomization/enrollment and must be completed up to 6 hours prior to or at the time of unclamping.

The study medication preparation and administration guidelines are described in a separate pharmacy manual. The subject will be weighed at the Baseline visit and this weight value will be used for the initial study medication preparation and the calculation of the dose. Most actual weight will serve as basis for further dose calculations.

All dosages prescribed and dispensed to the subject and all dose changes during the study must be recorded on the CFZ533 Dose Administration Record eCRF. Patients can be released after each treatment if deemed appropriate by the Investigator.

MMF administration

Mycophenolate mofetil will be 2 tablets of 500 mg or 4 capsules of 250 mg b.i.d. (2 g/day). For patients who remain intubated >24 hours post-transplant and/or whom are otherwise unable to swallow oral medication, IV MMF may be substituted until oral conversion is

possible.

The first dose of MMF will be administered immediately after randomization/enrollment and no later than 24 hours after graft reperfusion of the allograft or according to local practice.

Dose adjustment/interruption guidance for MMF is provided in [Appendix 4](#). All MMF doses and changes must be recorded on the MMF Dose Administration Record eCRF (Part 1) and Concomitant Medications eCRF under the Immunosuppressive category (Part 2).

Tacrolimus administration

Tac will be administered as PO capsules b.i.d. and adjusted to maintain within the target ranges of 4-11 ng/mL. Tac should be initiated as soon as possible and no later than 24 hours after reperfusion of the graft. The lowest permitted dosing of Tac in this study is 0.5 mg b.i.d. If Tac is discontinued for more than 21 consecutive days, and the study regimen cannot be maintained, the patient must be discontinued from the randomized treatment and managed per local practice. Subjects who discontinue their study regimen are expected to remain in the study on standard of care to Month 6 in Part 1 or Month 12 in Part 2.

Tac dosing will be modified by Investigators as needed and recorded on the Tacrolimus Dosage Administration Record (Part 1) and Concomitant Medication (Part 2) eCRF at each visit. In the event of Tac intolerance (e.g., nephrotoxicity, neurotoxicity) dose reduction of Tac may be necessary. If it occurs that the Tac trough level is outside the required target level, then the Investigator will be asked to confirm the intended Tac trough level, to record the start date and reason for dose reduction on the Tacrolimus Dosage Administration Record (Part 1) and Concomitant Medication (Part 2) eCRF.

The co-administration of drugs known to interfere with Tac metabolism (see [Appendix 5](#)) should be avoided if possible. If these drugs are required, the Investigator should carefully monitor Tac trough levels.

The patient will be instructed to record the time of the last dose on the day prior to the blood draw and to bring the morning dose to the visit so it may be administered after the blood sampling is completed.

Corticosteroids

CS will be administered according to local standard practice in a way that is consistent in all patients enrolled at each site. Dosing of CS should be recorded in the Concomitant Medications eCRF under the Immunosuppressive category.

5.5.5 Permitted dose adjustments and interruptions of study treatment

In general, symptomatic treatment should be considered first to treat patients who have difficulties to tolerate their immunosuppressive regimen. However, for patients who are still unable to tolerate the protocol-specified study treatment, dose adjustments and interruptions of study drugs are permitted in order to keep the patient on study treatment as follows below.

MMF/ MPA

Dose adjustment/interruption guidance for MMF is provided in [Appendix 4](#). All MMF doses and changes should be recorded on the MMF Dose Administration Record eCRF (Part 1) and Concomitant Medications eCRF under the Immunosuppressive category (Part 2).

MMF (e.g. Cellcept) is known to cause significant gastrointestinal side effects in some patients. In case of acute intolerance of MMF, other medications (e.g. Myfortic) can be given to reach target mycophenolate trough levels when used according to drug label and as per local practice at the clinical sites. Each case should be discussed individually with the Sponsor. At clinical sites where mycophenolates other than MMF (e.g. Myfortic) are being used as SoC, these drugs can be considered instead of MMF after discussion with the Sponsor.

Tacrolimus

Tac dosing will be modified by Investigators as needed and recorded on the Tacrolimus Dosage Administration (Part 1) and Tacrolimus Concomitant Medication (Part 2) eCRF at each visit.

CFZ533

No dose adjustments beyond changes based on the patient's weight are permitted to the CFZ533 dose during the study.

In case of notable AEs, SAEs including loss of efficacy and/or associated PK/PD data collected during the study, changes to the next planned dose level may be considered and implemented via an amendment.

Treatment of Acute Rejection Episodes

In all suspected acute rejection episodes, regardless of initiation of anti-rejection treatment, an allograft biopsy must be performed within 48 hours. Handling of biopsies is addressed in [Section 6.5.1](#).

All episodes of acute rejection must be entered on the corresponding eCRF (e.g., Acute Rejection eCRF, Kidney Allograft Biopsy eCRF) preferably within 24 hours. Sites should complete a SAE form for all confirmed acute rejection events in Part 1 and 2 and inform Sponsor within 24h.

Acute rejections should be treated with bolus methylprednisolone (other CS are acceptable at an equivalent dose) according to local practice. Recommended treatment is with at least 3 boluses of IV methylprednisolone with a minimal dose of 250 mg/bolus or at least 2 boluses of IV methylprednisolone with a minimal total dose of 750 mg.

Patients who experience steroid-resistant rejections, vascular rejections or rejections with a Banff grade \geq 2B ([Appendix 8](#)) should be discontinued from study treatment, converted to local SoC and may be treated with other anti-rejection therapies (i.e., antibody therapy).

All medications used for the treatment of suspected or confirmed acute rejections must be recorded on the Concomitant Medications eCRF under the Immunosuppressive category.

Management of signs of over-immunosuppression

CFZ533 was highly effective in preventing renal transplant rejection in NHP when used as monotherapy. Combining CFZ533 with MPA and CS after basiliximab induction may increase the risk for over-immunosuppression (e.g. BK viremia). For CFZ533 to be effective, full inhibition of CD40 signaling is required. Reducing the CFZ533 dose is not advisable, since under-dosing of CFZ533 may trigger loss of immunosuppression. In case of suspected over-immunosuppression clinical sites should first consider reducing the MPA level by 50 % or more (if MPA is completely stopped, CS may be slightly increased) with a follow up within the next weeks as per local practice. If there still are signs of over-immunosuppression, they should consider removing MPA and/ or reduce CS. If there still are signs of over-immunosuppression, or if the symptoms are severe, patient should be discontinued from CFZ533 and be switched to SoC.

Management of BK viremia

In case of diagnosed BK virus in urine, MPA levels should be reduced as a first measure as described in the Section above “Management of signs of over-immunosuppression”. Patients are considered to have significant BK viremia when their plasma PCR results report \geq 10,000 copies/mL of BK virus ([Sood et al 2012](#)).

If a patient is found to have BK viremia that reaches \geq 10,000 copies/mL in plasma, reducing/ stopping of MPA should be considered as a first measure. If patients have biopsy-proven BK nephropathy they should be discontinued from their randomized treatment and be switched to standard-of-care treatment as per local center practice.

Management of Patients with Delayed Graft Function (DGF)

DGF for this trial is defined as:

- A dialysis performed within 7 days of transplant
- ***excluding*** up to two dialysis sessions to correct electrolyte abnormalities (e.g., hyperkalemia) in the post-transplant time period

In case a patient experiences DGF, the DGF is by definition starting at reperfusion after the transplantation procedure. If the graft dysfunction is starting later according to the Investigator, then this condition is considered secondary graft dysfunction.

DGF must be reported as an AE for patients who experience DGF without requiring dialysis. In case DGF is reported as an AE and dialysis is also reported, the end of DGF is considered the day the last dialysis session ends.

In case of DGF, treatment will be according to local practice. DGF treatments must maintain

sufficient immunological coverage for the graft and may include maintaining, interrupting or reducing the dose of study drug and the use of anti-thymocyte globulin. If a polyclonal antibody or anti-thymocyte globulin is used, the study treatment must be discontinued and the subject will be placed on standard of care per local practice.

Primary graft non-function (PGNF) is defined as dialysis started 7 days after transplantation with a continuous record of post-transplant dialysis until either transplantectomy or death. PGNF should be reported on the Graft Loss eCRF.

If a subject is placed on permanent dialysis (or retransplanted), study treatment must be discontinued, the Graft Loss and Adverse Event eCRFs should be completed, and an SAE report of graft loss submitted. Dialysis treatments should be recorded on the Dialysis eCRF. Retransplantation should be recorded on the Surgical and Medical Procedures eCRF.

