8.5 Adjudication Committee

Not required for Part 1.

Since the study is open-label for investigators, for Part 2 an independent and blinded Adjudication Committee (AC) has been appointed in order to centrally evaluate all events reported as acute rejection, delayed graft function or other kidney dysfunction in an unbiased manner.

Details on the working procedures of the AC are described in a separate AC charter. An additional supportive PD analysis will be performed for BPAR and tBPAR based on adjudicated results.

9 Data analysis

Data from Part 1 and Part 2 will be presented separately.

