- “Was the rejection steroid resistant? = Yes” from the Rejection eCRF page

The date of event is the “Date rejection was first suspected” from Rejection eCRF page, or if missing the date of the first biopsy of the particular rejection episode.

Antibody-treated biopsy proven acute rejection

Antibody-treated biopsy proven acute rejections (BPAR with T-cell depleting therapy) are a subset of treated biopsy proven acute rejections. It is a clinically significant sub-component of treated BPAR as a marker of severity. An antibody-treated biopsy proven acute rejection is defined if the following criteria are fulfilled.

- Treated biopsy proven acute rejection and
- “Was antibody treatment administered = Yes” from the Rejection eCRF page

The date of event is the “Date rejection was first suspected” from Rejection eCRF page, or if missing the date of the first biopsy of the particular rejection episode.

Sub-clinical biopsy proven acute rejection

A sub-clinical biopsy proven acute rejection is defined as a BPAR *without* clinical suspicion of a rejection i.e. a biopsy was performed without the suspicion of an acute rejection (e.g. center-driven local-routine biopsy, protocol driven biopsy, etc.) but the result of that biopsy shows histological evidence of an acute rejection (Banff classification):

- BPAR and
- “Clinical suspicion of an acute rejection = No” on the Kidney Allograft Rejection eCRF or Reason for biopsy = “Routine biopsy per local practice” from the Biopsy page..

The date of event is the date of biopsy.

Graft Loss (GL)

The allograft will be presumed to be lost based on whichever of the following occurs first: the day the patient starts dialysis and is not able to subsequently be removed from dialysis, the day of transplantectomy, or the day irreversible loss of graft perfusion is demonstrated by appropriate imaging techniques. Primary graft non-function is a subset of graft loss.

A patient will be considered to have graft loss if in the Graft Loss eCRF page the following condition is met:

- “Has subject suffered a graft loss = Yes”

The date of graft loss is specified on the Graft Loss eCRF page. The date returned to regular dialysis or date of transplantectomy will be used if earlier.

Death

The endpoint death is derived from the Death eCRF page where also the date of death is captured.

Corporate Confidential Information

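### Protocol 5.5.5 sets a delayed graft function AE rule that its own definition empties, and a primary non-function start condition that excludes a graft dialysed from Day 1

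*Protocol*

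**What the plan says.** All the rules at issue stand together in Protocol 5.5.5, under the management of patients with delayed graft function.

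- **DGF definition for this trial:** "A dialysis performed within 7 days of transplant", with the exclusion of "up to two dialysis sessions to correct electrolyte abnormalities (e.g., hyperkalemia) in the post-transplant time period".
- **DGF onset:** "the DGF is by definition starting at reperfusion after the transplantation procedure". Dysfunction that the investigator judges to have begun later is called secondary graft dysfunction.
- **DGF reporting:** "DGF must be reported as an AE for patients who experience DGF without requiring dialysis". The next sentence opens "In case DGF is reported as an AE and dialysis is also reported" and goes on to fix the end date of DGF at the last dialysis session.
- **PGNF definition:** "Primary graft non-function (PGNF) is defined as dialysis started 7 days after transplantation", with unbroken dialysis up to transplantectomy or death. PGNF is to be entered on the Graft Loss eCRF.

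Two other places depend on these terms. Protocol 8.5 asks the blinded Adjudication Committee in Part 2 to "centrally evaluate all events reported as acute rejection, delayed graft function or other kidney dysfunction". SAP 6.2.1 states that "Primary graft non-function is a subset of graft loss" and, in the text available, gives PGNF no definition of its own.

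**The concern.** A site that follows 5.5.5 literally is told to report as a DGF adverse event only something that cannot be DGF under the trial's definition. For patients who do meet the definition, the section foresees an AE report but does not require one. Some sites may code these cases as DGF, some under another term, and some may regard the Dialysis eCRF entry as enough. The DGF line in the AE tables could then mix patients who do not meet the definition with an unknown share of those who do.

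This matters more than usual here. Protocol 3.2 accepts that investigator bias can affect patient management in an open-label study, and it justifies the population partly by its low risk of delayed graft function. Checking that premise, or comparing early graft function between Arms 2A and 2B, needs DGF to be counted in the same way everywhere. The PGNF wording creates a similar risk on the Graft Loss eCRF: the plainest case of a graft that never worked is shut out, and a later failure can be let in.

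**Working it through.** The plan states no figure on this point and no arithmetic applies. The check applies each rule, as written, to five courses a patient might follow.

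| Course after transplant | Meets DGF definition? | Covered by the DGF-specific AE rule? | Meets PGNF definition? | Graft loss (Protocol 6.5.1)? |
|---|---|---|---|---|
| A. Dialysis from Day 1 because the graft is not working; later recovers | Yes | No, dialysis was required | No | No |
| B. Poor function from reperfusion, never dialysed | No | Only if the site calls it DGF against the definition | No | No |
| C. One or two sessions, all for electrolytes | No, these are excluded | No | No | No |
| D. Continuous dialysis from Day 1 until transplantectomy | Yes | No, dialysis was required | No, as written | Yes |
| E. Graft works, first dialysis after a week, continuous until transplantectomy | No, onset is after reperfusion | No | Can be met | Yes |

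**DGF.** The definition needs at least one non-excluded dialysis session within 7 days. The AE rule needs DGF and no need for dialysis. No patient satisfies both. Course C does not rescue the rule: those patients were dialysed, and they do not have DGF. Courses A and D are DGF by definition, and no DGF-specific sentence requires an AE report for either. The end-date sentence is conditional on a report having been made and creates no duty to make one.

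**PGNF.** Whether the start condition means on the seventh day or from the seventh day onward, a Day 1 start does not satisfy it. Course D therefore fails. Course E can pass, although the onset rule in the same section would call it secondary graft dysfunction. Only if the wording is a slip for a start within 7 days would D pass and E fail, and the text does not say so.

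**What still captures these patients.** Protocol 6.2 and 7.1 require adverse events after consent to be recorded on the Adverse Event eCRF. Protocol 5.5.5 sends dialysis treatments to the Dialysis eCRF. Permanent dialysis counts as graft loss from the day it starts, whichever day that is (Protocol 6.5.1; SAP 6.2.1). Patients in courses A and D are thus recorded somewhere. What is unsettled is the label under which they are recorded.

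**What uses the two definitions.** The primary variable is tBPAR (Protocol 9.4.1; SAP 6.1.1). The composite is tBPAR, graft loss or death (SAP 6.2.1). The eGFR is calculated from measured creatinine, with zero imputed for a missing value after graft loss (Protocol 9.5.3.1; SAP 7.1.2). None of these takes DGF or PGNF as an input. The exposed outputs are the AE tables by arm, the PGNF entry on the Graft Loss eCRF, and the classification under which events go to adjudication.

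**The case against.** The strongest reply is that this is loose wording with a workable reading. Patients on dialysis already have a dedicated form and patients with dysfunction but no dialysis do not, so the AE page is named for the second group. The end-date sentence shows that the authors expected dialysis cases on the AE page too. This is plausible and shows that a capture route exists. It does not settle how cases are classified, because it uses DGF in a sense that the definition a few lines earlier rules out.

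A reader might also draw stronger conclusions, which the documents do not support:

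- **That patients with DGF on dialysis need not be reported as an AE at all.** The general AE rule covers them, and a case that prolongs hospitalization meets a seriousness criterion in Protocol 7.1.
- **That such cases will be lost to adjudication.** Protocol 8.5 speaks of reported events without saying reported as AEs, and it also covers other kidney dysfunction. Biopsies for suspected rejection and other kidney disease related events go to the committee as well (Protocol 6.5.1). The committee's charter is a separate document that is not available here. Inconsistent referral under the DGF label is possible; loss is not shown.
- **That the eGFR comparison or the proof-of-concept decision is distorted.** Neither uses these definitions. The rule in 5.5.5 that ends study treatment when a polyclonal antibody or anti-thymocyte globulin is used depends on what was given, and not on how the event was coded.
- **That a planned PGNF analysis would contain the wrong patients.** No such analysis is visible. Parts of the SAP are redacted, so neither its absence nor the absence of a DGF derivation can be asserted.

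**Conclusion.** The point holds as an internal contradiction in Protocol 5.5.5, in two parts. The only mandatory AE rule specific to DGF applies to nobody under the trial's definition. The PGNF start condition, read as written, excludes a graft dialysed continuously from Day 1 and can admit one whose failure the same section calls secondary. Nothing visible elsewhere in the protocol or SAP repairs either rule.

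The consequence is inconsistent classification of DGF and PGNF across sites, and possibly between arms in an open-label comparison. Primary tBPAR, total graft loss and eGFR are unaffected. The number of the approximately 45 Part 2 patients involved cannot be estimated, because the documents give no DGF rate, and the direction of any difference between arms is unknown. The conclusion assumes that sites apply the written text. If training material or the adjudication charter already corrects it, the practical effect is smaller, but the protocol wording still needs to be reconciled. This should be corrected; it does not threaten the main conclusions of the trial.

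**What to change.** 1. Reconcile the DGF sentences in Protocol 5.5.5 so that the DGF-specific AE rule covers patients who meet the trial's own DGF definition, in the same way in both arms. Record dysfunction without dialysis under a distinct term, so that the two groups can be tabulated apart.
2. Bring the PGNF start condition into line with the rule that DGF begins at reperfusion. The documents do not show which wording was meant, so the sponsor should confirm it.
3. In the SAP, tabulate DGF by arm from the Dialysis eCRF, using session dates and, where recorded, the reason for dialysis, instead of AE terms. If the reason is not recorded, the definition still gives bounds. Because at most two sessions can be excluded, a patient with three or more sessions within 7 days has at least one that counts, and a patient with one or two is undetermined. The number of patients with at least three sessions is then the lower bound, and the number with at least one is the upper bound.

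The cost is a wording change and a small amount of programming on data already collected. The reported DGF count may rise. No change to treatment or visits is involved.

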Investigational drug	The study drug whose properties are being tested in the study; this definition is consistent with US CFR 21 Section 312.3 and is synonymous with “investigational new drug” or “investigational medicinal product”.
Investigational treatment	All investigational drug(s) whose properties are being tested in the study as well as their associated treatment controls.
	This includes any placebos, any active controls, as well as approved drugs used outside of their indication/approved dosage or tested in a fixed combination.
	Investigational treatment generally does not include other treatments administered as concomitant background therapy required or allowed by the protocol when used within approved indication/dosage.
Medication number	A unique identifier on the label of each study drug package in studies that dispense study drug using an IRT system.
Subject number	A number assigned to each subject who enrolls in the study. When combined with the center number, a unique identifier is created for each subject in the study.
Period	A minor subdivision of the study timeline; divides phases into smaller functional segments such as screening, baseline, titration, washout, etc.
Premature subject withdrawal	Point/time when the subject exits from the study prior to the planned completion of all study assessments.
Randomization number	A unique identifier assigned to each randomized subject, corresponding to a specific treatment arm assignment.
Stage	A major subdivision of the study timeline; begins and ends with major study milestones such as enrollment, randomization, completion of treatment, etc.
Study completion	Point/time at which the subject came in for a final evaluation

visit.

Study drug/treatment	Any drug (or combination of drugs) administered to the subject as part of the required study procedures; includes investigational drug, active drug run-ins or background therapy: CFZ533 + tacrolimus and CFZ533 + mycophenolate mofetil
Study drug discontinuation	Point/time when subject permanently stops taking study drug (any component of the regimen) for any reason.
Subject	An individual who has consented to participate in this study. The term Subject may be used to describe either a healthy volunteer or a patient.
Variable	Information used in the data analysis; derived directly or indirectly from data collected using specified assessments at specified time-points.

Corporate Confidential Information

Corporate Confidential Information

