5.5.9 Prohibited treatment

Immunosuppressants other than those specified in the protocol are NOT allowed after informed consent up to the end of study. If the use of any of these medications or other non-protocol immunosuppressants is discovered prior to randomization/enrollment, the subject must not be randomized and will be recorded as a screen failure. If discovered after randomization/enrollment, no further doses are to be given, and the subject should continue on the randomized/assigned treatment regimen, noting the protocol deviation.

The exception is for the treatment of acute rejection not responding to corticosteroids.

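### Section 5.5.5 gives sites two incompatible instructions on reducing CFZ533 in a patient with delayed graft function, and the conflict falls in the loading phase

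*Protocol*

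**What the plan says.** All of the main conflict lies in Protocol Section 5.5.5, read with the glossary.

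- **DGF paragraph.** Treatment follows local practice and must keep enough immunological cover for the graft. It "may include maintaining, interrupting or reducing the dose of study drug and the use of anti-thymocyte globulin". The next sentence adds: "If a polyclonal antibody or anti-thymocyte globulin is used, the study treatment must be discontinued", with the patient moved to standard of care.
- **Glossary, entry for study drug/treatment.** The term "includes investigational drug, active drug run-ins or background therapy", and the entry goes on to name CFZ533 combinations.
- **CFZ533 paragraph.** "No dose adjustments beyond changes based on the patient's weight are permitted to the CFZ533 dose during the study".
- **Over-immunosuppression paragraph.** "Reducing the CFZ533 dose is not advisable, since under-dosing of CFZ533 may trigger loss of immunosuppression".
- **Lead-in to the section.** For patients who cannot tolerate treatment, "dose adjustments and interruptions of study drugs are permitted in order to keep the patient on study treatment as follows below". Adjustments and interruptions are named as two things.

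Section 5.5.9 bans immunosuppressants that the protocol does not specify and names one exception, acute rejection that does not respond to corticosteroids. If a banned agent is discovered after randomization, it is stopped and "the subject should continue on the randomized/assigned treatment regimen, noting the protocol deviation".

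**The concern.** An investigator with a DGF patient in Arm 2A who looks up whether CFZ533 may be reduced finds a permission in one paragraph and a prohibition in another, with nothing to say which governs. Each has a claim to be the more specific rule: the DGF paragraph is specific to the situation, the CFZ533 paragraph to the drug.

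Two things are at stake. The first is patient safety: the protocol itself warns that "under-dosing of CFZ533 may trigger loss of immunosuppression". The second is interpretation. Part 2 is meant to test one fixed CFZ533 regimen in about 30 patients. If sites resolve the conflict differently, similar patients receive different loading exposure for reasons the plan did not intend.

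The ATG text raises a smaller question of the same kind. Section 9.4.2 counts only events on treatment, so the rule that decides whether a patient leaves study treatment also bears on whether a later rejection is counted.

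**Working it through.** This is mainly a comparison of texts. Arithmetic is needed only for the timing.

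**1. Reproduce the plan's dose count.** Section 3.1.4 gives Day 1, then Days 3, 7, 15, 29, 43 and 57, then monthly to about Day 337. A study month is 28 days (Section 3.1.2).

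- Loading doses: Days 1, 3, 7, 15, 29, 43, 57 = 7, as Section 3.3 states.
- Monthly doses, Day 85 to Day 337: (337 − 85)/28 + 1 = 252/28 + 1 = 10.
- Total: 7 + 10 = 17, as Section 5.2 states.

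**2. Place DGF on that schedule.** Transplantation is Day 1. DGF requires dialysis in the first 7 days and is dated from reperfusion. The Day 1 dose must be complete by unclamping, so it is given before DGF can begin. The Day 3 and Day 7 doses fall inside the window.

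| Decision taken after the dose on | Loading doses still to come |
|---|---|
| Day 1 | 7 − 1 = 6 |
| Day 3 | 7 − 2 = 5 |
| Day 7 | 7 − 3 = 4 |

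A CFZ533 decision prompted by DGF is therefore a loading-phase decision.

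**3. Set the instructions for CFZ533 in DGF side by side.**

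| Action | DGF paragraph, with glossary | CFZ533 paragraph | Over-immunosuppression paragraph |
|---|---|---|---|
| Maintain | allowed | consistent | consistent |
| Reduce | allowed | not permitted, except for weight | not advised |
| Interrupt | allowed | not addressed | not addressed by name |

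The reduction row is a direct contradiction. The interruption row is not: the lead-in separates interruptions from adjustments, and the CFZ533 sentence bars only adjustments. Protocol Section 9.3.1 and SAP Section 7.1.2 also expect temporary interruptions of study medication and keep those days in the treatment duration.

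**4. Set the ATG instructions side by side.** Under the DGF paragraph, ATG may be used and study treatment then stops. Under Section 5.5.9, the only named exception is steroid-resistant rejection, and a patient found on a banned agent stays on the assigned regimen. If a site takes ATG for DGF to be banned, the two instructions are opposite. If it takes the DGF paragraph as specifying ATG, Section 5.5.9 is not triggered.

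**5. What cannot be computed.** The documents give no DGF rate, the CFZ533 pharmacokinetic simulations are blacked out, and so is the on-treatment window in Section 9.4.1. No effect on exposure, rejection or the proof-of-concept result can be derived.

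**The case against.** The best case for the text is that the CFZ533 paragraph is the rule for that drug, while the DGF paragraph is general wording for both parts and both arms and so also covers tacrolimus and MMF. The DGF paragraph requires enough immunological cover, which restrains under-dosing. Section 3.2 says the population was chosen for low risk of complications, DGF included. All of this is fair and makes a harmful outcome less likely. None of it tells a site that CFZ533 is outside the DGF sentence, and the glossary says it is inside the term used there.

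On ATG the objection largely succeeds. Section 5.5.9 bans agents that the protocol does not specify, and the DGF paragraph specifies ATG and states the consequence. What stands is that the exception sentence in 5.5.9 omits DGF.

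A reader might infer more than the documents support:

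- **A large exposure loss.** Four doses to Day 15 total 4 × 10 = 40 mg/kg. Missing Day 7 removes 10/40 = 25%, and missing Days 3 and 7 removes 20/40 = 50%. These are interruptions, for which the conflict is only ambiguous, and mg/kg sums are not concentrations.
- **A count of affected patients.** Assuming a DGF rate of 10–25%, 30 patients would give 3 to 7.5 with DGF. The rate is an assumption, and not every DGF patient would have CFZ533 changed, since maintaining the dose is one of the listed options.
- **A changed proof-of-concept result.** With 30 and 15 patients and 1 control event, the posterior probability of a difference below 0.20 is 0.642 at 7 CFZ533 events (criterion met) and 0.496 at 8 (not met). This shows that the rule can turn on one event, not that this wording would cause one.
- **ATG as a route to under-dosing on treatment.** It is not, because its use ends study treatment.

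**Conclusion.** The contradiction is real for one action: reducing CFZ533 in DGF. It rests on the glossary definition applying to the DGF sentence, and nothing in that sentence says otherwise. For interruption the text is unclear rather than contradictory. For ATG there is an arguable mismatch between the DGF paragraph and the exception in Section 5.5.9.

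The timing is certain: a decision inside the DGF window comes with 4 to 6 loading doses outstanding. The consequence for exposure or rejection cannot be sized from the documents and should not be given a number. The point deserves correction because it concerns dosing safety and consistent handling within Arm 2A, and because the correction is cheap.

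**What to change.** 1. In the DGF sentence of Section 5.5.5, replace the general term with the named drugs. State separately which may be reduced and which may be interrupted, and say whether CFZ533 is among them for each.
2. Make the CFZ533 and over-immunosuppression paragraphs give the same answer.
3. Align the exception in Section 5.5.9 with the ATG sentence in the DGF paragraph, so that one rule decides whether the patient leaves study treatment.
4. List CFZ533 doses changed or missed because of DGF by patient. Section 5.5.4 already requires dose changes to be recorded with reasons, and SAP Section 7.1.2 already summarises them by reason.

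Which clinical rule applies is for the sponsor's medical lead; this review takes no position. Do not re-run the proof-of-concept criterion without the affected patients: that would drop Arm 2A patients on a post-randomization event with no matching exclusion in the control arm.

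The cost is a wording amendment with its usual approvals and one listing. No new data are needed, and the sample size and decision rule are unchanged.
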